9.3 VARIABLES

9.3.1 Exposures

- *Exposure: Tiotropium/Olodaterol (Spiolto®).*
- *Reference: Tiotropium (Spiriva®).*

Both groups will be identified according to brand name as the first of two prescriptions of the respective drug within 60 days. Given the limited information on treatment duration in the MDV data, a days supply of 14 days will be assumed for “*Spiolto Respimat 28puffs*.” Otherwise, 30 days will be assumed for “*Spiriva Inhalation Capsules 18microg*”, “*Spiriva 2.5microg Respimat 60puffs 150microg*”, “*Spiolto Respimat 28puffs*” and “*Spiolto Respimat 60puffs*”. A grace period of 14 days between assumed end of days supply and subsequent prescription will be used as an allowable gap.

9.3.2 Outcomes

9.3.2.1 Primary outcomes

Triple Therapy Use

[figure not shown]
The primary outcome of interest is incident rate of triple therapy initiation (first event per patient) defined as any LAMA/LABA/ICS fixed dose combination or any concurrent use for 30 consecutive days of the following:

- any LAMA/LABA fixed dose combination + any ICS single formulation
- any LAMA single formulation + any LABA/ICS fixed dose combination
- any LAMA single formulation + any LABA single formulation + any ICS single formulation

MDV data has limited information on treatment duration with the days of prescription recorded as 1 day for most patients. Therefore, a days supply of 30 days will be assumed. Although we will require at least 30 days of overlap, the first date of triple therapy overlap will serve as the outcome event date, as corresponds to the initiation of triple therapy. Looking into the future to satisfy the requirement of overlap for at least 30 days has the potential to inflict immortal person-time, but is necessary to differentiate concurrent use when subsequent medication is added (see [Figure 3](#) - example Patient A) from an early sequential prescription fill when subsequent medication is switched to (see [Figure 3](#) - example Patient B).

Figure 3

Illustration of outcome

Censoring

Patients will be censored if they had an occurrence of any of the following: outcome (initiation of triple therapy), death, or end of data. The analysis will use an intention-to-treat censoring approach, which does not account for treatment change. A sensitivity analysis will employ an as-treated censoring approach to further censor upon discontinuation of index therapy or initiation of the other index treatment arm. Thus, events will be assigned to exposure groups according to that patient's original index medication, even if that patient discontinued or crossed over.

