8. RESEARCH QUESTION AND OBJECTIVES

To compare the early intervention effectiveness of Tio/Olo vs. Tio among COPD patients.

The primary objective of this study is to:

- Compare time to LAMA/LABA/ICS triple therapy initiation among initiators of Tio/Olo vs. initiators of Tio.

The secondary objectives of the study are to compare the following among initiators of Tio/Olo vs. initiators of Tio:

Secondary outcomes

- Time to First Moderate or Severe COPD Exacerbation
 - Time to First Moderate COPD Exacerbation
 - Time to First Severe COPD Exacerbation
- Number of Moderate or Severe COPD Exacerbations
 - Number of Moderate COPD Exacerbations
 - Number of Severe COPD Exacerbations

Further endpoints:

- All-Cause Mortality,
- Number of Unique Pulmonary Medication Prescriptions
- Number of Hospitalizations for a Respiratory Condition
- Major Cardiovascular Adverse Events (MACE)
- Home oxygen therapy (HOT)

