9.2.2 Study population

The study cohort will include all patients who initiate Tiotropium/Olodaterol (Tio/Olo) or Tiotropium (Tio) during the patient selection period. Initiation (new use) will be determined based on no prescription claims for Tio/Olo or Tio during the baseline period or during all available data prior to cohort entry date. All patients will additionally be required to have a second claim for the index medication within 60 days after cohort entry to ensure primary adherence of index therapy.

The following exclusion criteria will then be applied to generate the unmatched cohort:

- Aged <40 years on cohort entry.

[figure not shown]
Proprietary confidential information © 2020 Boehringer Ingelheim International GmbH or one or more of its affiliated companies

- Any LAMA, LABA, ICS maintenance therapy (alone or in combination) during the 180-day baseline period prior to cohort entry for maintenance treatment and not cough, i.e. duration >30 days, or any prescription within the 30 days prior to cohort entry.
- Patients without continuous enrolment (days since first inpatient/outpatient encounter in the data) during the baseline period.
- No prior diagnosis of COPD [ICD-10: J41*, J43*, J44* and doubt (UTAGAIFLG) = 0 (no)]
- Patients without a second prescription claim of their index medication within 60 days after the cohort entry date.
- Diagnosis of asthma [ICD-10: J45* and doubt (UTAGAIFLG) = 0 (no)] during the baseline period.
- Diagnosis of lung cancer [ICD-10: C34*, D02.2, Z80.1, Z85.1 and doubt (UTALAIFLG) = 0 (no)] or lung transplant (Health claim code: 150317670, 150322510, 150322610, 150336510, 150336610, 150336710, 150399270) prior to the cohort entry date using all available data.
- Patients who initiate both Tio/Olo and Tio simultaneously on the cohort entry date.
- Any use of triple therapy (LAMA + LABA + ICS) during the baseline period or between the cohort entry date and 1 day prior to the start of follow-up.

All patients will be selected into the first treatment arm (Tio/Olo or Tio) that they qualify for and will not be allowed to re-enter the cohort by design.

The cohort will then be used to construct two matched cohorts (not mutually exclusive) according to the: 1) basic propensity scores and 2) high dimensional propensity scores

Figure 2 Depicts the flow diagram of patients.

Basic Propensity Score Matching

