9.7.3 Sensitivity Analyses

1. Less Stringent Qualifying Event Criterion

Instead of defining the event to qualify patients for inclusion based on two prescriptions within 60 days, patients may enter upon only one prescription. While some confidence is lost in whether the patients truly took their index medications, the less stringent qualifying event criterion will allow more patients to be included, increasing statistical power. Furthermore, the possibility of immortal time bias is also mitigated, since the time between prescriptions is no longer present.

2. As-treated Censoring

The analysis will use an as-treated approach for primary, secondary and further endpoint outcomes. In addition to the censoring criteria mentioned for the intention-to-treat approach (outcome, death, or end of data), patients will also be censored after medication discontinuation or switching over to the other arm.

3. Alternative algorithm for COPD

The analysis will use a different set of diagnosis codes for COPD (J43*, J44*) when selecting COPD patients. Compared to the primary analysis, this algorithm omits the diagnostic code for chronic bronchitis (J41*), as this code is commonly used by pulmonologists when prescribing Mucodyne to patients who do not actually have chronic bronchitis. While some true chronic bronchitis patients may be excluded, the selection of patient will increase specificity.

4. Asthma patients with doubt

Asthma patients with doubt are defined as patients with a diagnosis code for asthma and without evidence of any asthma specific treatment (ie., ICS, ICS/LABA). This sensitivity analysis will include patients identified with asthma with doubt.

5. ACOS sensitivity analysis

Patients that have evidence of asthma during the follow-up period will have their data censored on the date of asthma diagnosis during the follow-up period. This will ensure that they contribute information during their COPD disease trajectory up until the time they develop asthma. This approach will mitigate introducing immortal time bias for those patients with ACOS during the follow-up period.

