9.9 LIMITATIONS OF THE RESEARCH METHODS

This study will be conducted using hospital-based health insurance claims following the DPC payment system and is subject to certain limitations. One limitation is that these are based on a large, non-random convenience sample based in Japan, which may contain biases or lack generalizability to other populations. Data also come from a subset of hospitals in Japan, which would lead to failure to record events if patients visit medical centers not included in MDV's data sources (**Tanaka 2015**). Moreover, because healthcare is nationalized in Japan, the notion of enrolment is not applicable, and all patients are assumed to be observable throughout the global date range of the data. However, if a patient's emigration or mortality is not captured, then they would remain in the study despite not truly being eligible for any events, thereby leading underestimations of the risks and rates and possible bias in the hazard ratio if these patients are differentially distributed between the exposed and unexposed groups.

Another limitation of the study is that patients on monotherapy may escalate to double therapy before receiving the triple therapy. The patients starting on double therapy do not have this option. Therefore, patients on monotherapy may take longer to get to triple therapy than the patients on double therapy.

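### A LABA/ICS inhaler added to the continued index drug counts as a primary event on Tio but not on Tio/Olo, and no planned analysis shows the effect on the hazard ratio

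*Combined protocol and SAP*

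**What the plan says.** The primary objective in Section 8 is to "Compare time to LAMA/LABA/ICS triple therapy initiation among initiators of Tio/Olo vs. initiators of Tio". Section 9.3.2.1 and the abstract define the event as a triple FDC or 30 days of concurrent use of one of three combinations:

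- "any LAMA/LABA fixed dose combination + any ICS single formulation"
- "any LAMA single formulation + any LABA/ICS fixed dose combination"
- three separate single-agent inhalers, one from each class.

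The list is closed and specific to formulation. The 30-day overlap, according to the same section, "is necessary to differentiate concurrent use when subsequent medication is added" from an early fill of a drug to which the patient is switching. The primary analysis uses an "intention-to-treat censoring approach, which does not account for treatment change".

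Section 9.2.2 excludes patients with any triple therapy at baseline or "between the cohort entry date and 1 day prior to the start of follow-up". There, triple therapy is described by class, with no restriction on formulation.

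Of the five sensitivity analyses in Section 9.7.3, the as-treated one changes censoring only: "patients will also be censored after medication discontinuation or switching over to the other arm". The other four change the entry rule, the COPD codes and the handling of asthma. Section 9.7.2 plans no subgroup analyses. On the concurrent-use algorithm, Section 9.12 discusses only the need to look ahead.

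**The concern.** The missing combination is LAMA/LABA FDC plus LABA/ICS FDC. Only a patient on a LAMA/LABA FDC can reach triple therapy that way, and every Tio/Olo patient starts on one. Whether the same added inhaler is recorded as an event therefore depends on the index product. Propensity score matching balances baseline covariates and cannot correct outcome ascertainment that differs by exposure. A missed patient also stays at risk and adds person-time, so the rate, the risk and the hazard ratio are all affected.

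The direct effect is to lower the hazard ratio for Tio/Olo against Tio. There is also an opposite effect. Section 9.9 expects that "patients on monotherapy may escalate to double therapy before receiving the triple therapy", and under intention-to-treat follow-up a Tio patient who has stepped up to a LAMA/LABA FDC falls into the same gap. The net direction is unknown, and the plan contains nothing that would reveal it.

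**Working it through.** **1. The plan's own figures.** Section 9.5 assumes 1-year rates of 6% (Tio/Olo) and 10% (Tio), HR 1.73, two-sided alpha 0.05, 90% power and 141 events. Schoenfeld's formula with 1:1 allocation gives 4 × (1.960 + 1.282)² / (ln 1.73)² = 140, which agrees with 141. For Tio/Olo against Tio, the assumed rates give a planned HR of ln(0.94)/ln(0.90) = 0.587. (Its inverse is 1.70, the abstract's value; Section 9.5 has 1.73.)

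**2. Which combinations are listed.** Section 9.3.2.1 names five product types besides the triple FDC: LAMA, LABA, ICS, LAMA/LABA and LABA/ICS. Four minimal sets cover all three classes:

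| Set | Listed? |
|---|---|
| LAMA/LABA + ICS | yes |
| LAMA + LABA/ICS | yes |
| LAMA + LABA + ICS | yes |
| LAMA/LABA + LABA/ICS | **no** |

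**3. One-product additions to a continued index drug that complete the three classes.**

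| Index drug | Addition | Event? |
|---|---|---|
| Tio | LABA/ICS | yes |
| Tio/Olo | ICS | yes |
| Tio/Olo | LABA/ICS | **no** |

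**4. Effect on the hazard ratio.** Let f and g be the shares of escalations missed in the Tio/Olo and Tio arms, and r1 and r0 the shares of those missed patients who later meet a listed combination. The documents give none of these, so all four are assumptions. Approximately, the HR is multiplied by

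(1 − f(1 − r1)) / (1 − g(1 − r0)).

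The rejection rate under a true HR of 1 with 141 events is Φ(−1.96 + s) + Φ(−1.96 − s), where s = |ln factor| × √141 / 2. With r1 = r0 = 0:

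| f | g | Factor | Planned HR 0.587 becomes | Rejection if true HR = 1 |
|---|---|---|---|---|
| 0 | 0 | 1.00 | 0.587 | 5.0% |
| 10% | 5% | 0.90/0.95 = 0.947 | 0.556 | 6.2% (s = 0.32) |
| 10% | 0 | 0.900 | 0.529 | 9.6% (s = 0.63) |
| 20% | 0 | 0.800 | 0.470 | 26.3% (s = 1.32) |
| 5% | 10% | 0.95/0.90 = 1.056 | 0.620 | 6.2% (s = 0.32) |

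Whenever f = g, the factor is 1.00. The row with f = 20% and g = 0 is an extreme.

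**5. Later qualification.** At f = 10% and g = 5%:

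- r1 = 0.5, r0 = 0: 0.95/0.95 = 1.00
- r1 = 0, r0 = 0.5: 0.90/0.975 = 0.92

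**6. A larger matched cohort.** If all 1,829 Tio/Olo users were matched, there would be 3,658 patients. With true rates of 10% a year in both arms, f = 10%, g = 0 and one year of follow-up, the recorded events are 1,829 × (0.0905 + 0.10) ≈ 348. Then s = 0.105 × √348 / 2 = 0.98, and the rejection rate is 16.6%. More events make the same distortion more likely to produce a significant result.

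**The case against.** The strongest counter-argument is that the omission may be intended. The unlisted combination is the only one of the four that duplicates a class (the LABA), and leaving it out is consistent with counting only non-duplicative regimens. That is possible, but the protocol does not say so, and a deliberate exclusion would still need a stated reason and a check of its effect.

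Second, nothing in the documents shows how often a LABA/ICS inhaler is added to a continued LAMA/LABA FDC. This stands: f and g are assumed, and f = 0 cannot be ruled out. Tio/Olo patients who move to a triple FDC, add a single ICS, or change to a single LAMA with LABA/ICS are all counted. Only additions to a continued LAMA/LABA FDC are lost.

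Third, the moderate cases are small. With 141 events the standard error of the log HR is about 2/√141 = 0.168, so the 95% half-width is 0.33. A factor of 0.947 shifts the log HR by 0.054, about one-sixth of that. This also stands. It limits the severity, but a systematic shift does not shrink as events accumulate.

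Fourth, a fourth combination would not make ascertainment fully equal. The 14-day grace period may let an early switch reach 30 days of overlap. Section 9.3.1 lists the 28-puff Spiolto pack under both 14 and 30 days' supply, while Section 9.6 gives 14. These passages need reconciling, but they affect the combinations already listed too and are a separate matter. Figure 3 is not visible in the text available; it is cited for adding versus switching and probably does not settle this point.

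**Conclusion.** The concern holds. The omission and the resulting difference between arms follow directly from the wording of Section 9.3.2.1, and no planned analysis in Section 9.7.3 would show its effect on the primary hazard ratio. The permission in Section 9.8 to modify measure definitions is not a planned analysis.

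Size and net direction are uncertain. Over the assumed range the hazard ratio is multiplied by 0.80 to 1.06, and the less extreme cases lie between 0.90 and 1.06. These factors treat missed patients as never qualifying later; later qualification moves the factor up or down depending on the arm in which it occurs. This should be fixed: the defect is in the primary endpoint, its effect is unmeasured, and the remedy is cheap.

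**What to change.** Add LAMA/LABA FDC with LABA/ICS FDC as a fourth combination in Section 9.3.2.1 and the abstract, under the same 30-day overlap rule. Tabulate events by route and arm, and report the three-item definition as a sensitivity analysis. If the omission is deliberate because the LABA is duplicated, say so in one sentence, keep the three-item list as primary, and run the four-item definition as the sensitivity analysis. Either way, record the choice in an amendment before outcomes are compared by arm.

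A class-based rule (30 consecutive days covered by LAMA, LABA and ICS from any products) is a slightly broader alternative. It is not equivalent: 15 days of LAMA + LABA/ICS followed by 15 days of LAMA/LABA + ICS would satisfy it, yet no single listed combination lasts 30 days.

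In Section 9.2.2, keep the broad wording of the triple-therapy exclusion and clarify only that it includes this combination. This matters mainly between cohort entry and the second fill, because the other exclusions already cover most baseline use.

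The cost is one line of definition or one sentence of justification, a small code change, one table and one extra analysis, all on data already held. The downside is that some duplicate-LABA product switches may be counted as events; the overlap rule limits this.

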9.6 DATA MANAGEMENT

Dataset

The Medical Data Vision dataset is comprised of administrative records of longitudinal inpatient, outpatient and drug data from multiple hospitals that have been standardized and de-identified prior to use for the analysis. The statistical analysis will be conducted using the

COPD Maintenance Therapy Drug Duration

Given limited information on treatment duration in the MDV data, a days supply of 14 days will be assumed for “Spiolto Respimat 28puffs.” Otherwise, 30 days will be assumed for all LAMA, LABA, and ICS maintenance therapies, including “Spiriva Inhalation Capsules 18microg”, “Spiriva 2.5microg Respimat 60puffs 150microg”, “Spiriva 1.25microg Respimat 60puffs 75microg”, and “Spiolto Respimat 60puffs”. A grace period of 14 days between assumed end of days supply and subsequent prescription will be used as an allowable gap.

Handling of Missing Data

Missing data that occurs in covariates or descriptive variables will be classified as its own level (i.e. missing data indicator). In addition, a feasibility assessment before beginning the

analyses will be done, and variables with >75 % missing values will be excluded from all analyses, other than baseline characteristics. If a variable is left with only one level other than missing, the variable will be excluded completely from all analyses.

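### The primary-outcome overlap rule in 9.3.2.1 assumes 30 days' supply throughout and omits the 14-day exception for Spiolto Respimat 28puffs given in 9.3.1 and 9.6; 9.3.1 also lists that pack under both values.

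*Combined protocol and SAP*

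**What the plan says.** Three sections of the protocol set a days' supply.

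- **Section 9.3.2.1 (primary outcome).** Noting that recorded treatment duration is poor, it states: "Therefore, a days supply of 30 days will be assumed". No product is excepted and no other section is cited. Unless a triple fixed-dose product is used, an event needs 30 consecutive days of concurrent use. The dating rule is: "Although we will require at least 30 days of overlap, the first date of triple therapy overlap will serve as the outcome event date". One qualifying route is a LAMA/LABA combination with a separate ICS, and Spiolto feeds that route.
- **Section 9.3.1 (exposures).** It states "a days supply of 14 days will be assumed for “*Spiolto Respimat 28puffs*.” Otherwise, 30 days will be assumed for" a list of named products. That list ends with "Spiolto Respimat 28puffs*” and “*Spiolto Respimat 60puffs", so the 28-puff pack appears under both values.
- **Section 9.6 (drug duration for COPD maintenance therapy).** It states "a days supply of 14 days will be assumed for “Spiolto Respimat 28puffs.” Otherwise, 30 days will be assumed for all LAMA". The same sentence goes on to cover maintenance products of the LABA and ICS classes. Its named 30-day products end with "Spiriva 1.25microg Respimat 60puffs 75microg”, and “Spiolto Respimat 60puffs"; the 28-puff pack is not among them.

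Sections 9.3.1 and 9.6 also allow a 14-day gap between the end of supply and a subsequent prescription. Section 9.3.2.1 does not mention it.

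Two further rules bear on the point. Section 9.2.1 starts follow-up at the second qualifying prescription. Section 9.2.2 excludes patients with triple therapy between cohort entry and the day before follow-up starts.

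**The concern.** The assumed supply decides whether the 30-day threshold is reached. An analyst who programs the outcome from 9.3.2.1 alone credits a 28-puff fill with 30 days. One who works from 9.6 credits it with 14. The same records can then give an event under one reading and none under the other.

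The ambiguity is not balanced between arms. The pack is a Tio/Olo product, so it falls mainly on Tio/Olo initiators, plus any Tio initiators who later move to it. It also has a direction. In a patient who is included under either value, the days covered at 30 days' supply contain all those covered at 14, so the longer value can only add an event or bring one forward.

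It also bears on the stated purpose of the overlap test, which the protocol calls "necessary to differentiate concurrent use when subsequent medication is added", as opposed to a switch. Crediting a pack with 16 more days (30 − 14) makes some short overlaps look like sustained concurrent use.

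**Working it through.** **Inputs.** Overlap needed: 30 consecutive days (9.3.2.1). Supply of the 28-puff pack: 14 days (9.6 and the first statement in 9.3.1) or 30 days (9.3.2.1 read literally). ICS supply: 30 days (9.3.2.1 and 9.6). The plan gives no figure of its own to reproduce here.

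**Assumptions, because the documents give no refill or pack-quantity data.** One pack per fill, refills every 14 days, no stockpiling, and no later move to another LAMA/LABA pack. Day 0 is the fill of the pack during which ICS is added, and that pack is filled at or after the start of follow-up (the second qualifying fill or later). ICS is first filled on day k, with k from 0 to 13, and filled once. Refills are on time and none follows the last pack, so no grace days enter.

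**Formulae.** With m packs counted from day 0:

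- covered days are 14m at 14 days' supply, and 14(m − 1) + 30 at 30 days' supply;
- overlap is the smaller of 30 and (covered days − k).

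| Packs from the add-on pack (m) | Covered days, 14 v 30 | Overlap at 14 days' supply | Overlap at 30 days' supply | Add-on days on which event status differs |
|---|---|---|---|---|
| 1 (no further pack) | 14 v 30 | 14 − k | 30 − k | 1 of 14 (k = 0: 14 v 30) |
| 2 (one further) | 28 v 44 | 28 − k, so 15 to 28 | 30 | 14 of 14 |
| 3 (two further) | 42 v 58 | 30, but 29 at k = 13 | 30 | 1 of 14 |
| 4 (three further) | 56 v 72 | 30 | 30 | 0 of 14 |

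A second ICS fill leaves the last column unchanged; in the second row the overlap becomes 28 − k v 44 − k.

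**Late refills.** These can widen the difference. With two packs 30 days apart and continuous ICS from day 0, the gap at 14 days' supply is 30 − 14 = 16 days, longer than the 14-day allowance. The longest overlap is then 14 days, against 60 at 30 days' supply. The documents do not show how often this happens.

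**Grace period.** Even if 14 grace days were added to a single pack, 14 + 14 = 28 days is still below 30.

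**ICS added between the first and second index fills.** This time precedes follow-up. Triple therapy recognised there leads to exclusion under 9.2.2 in the main analysis, so the days' supply can affect who is included, not how many events are counted.

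**Duplicate entry in 9.3.1.** For a given last pack, the as-treated discontinuation date could move by 30 − 14 = 16 days. This matters only in sensitivity analysis 2, where "patients will also be censored after medication discontinuation or switching over to the other arm". The primary intention-to-treat analysis does not censor on discontinuation.

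**The case against.** The strongest answer is that 9.6 already settles the matter. It has its own heading for drug duration and covers LABA and ICS products, which are not study exposures and enter the plan mainly through the triple-therapy outcome and the prior-therapy exclusions. A rule that covers them is naturally read as governing the outcome, with the sentence in 9.3.2.1 as shorthand for the default. The duplicate in 9.3.1 also looks like a list slip: 9.6 has the Spiriva 1.25 microgram product in the corresponding place, and 9.3.1 omits it.

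Most of this stands, and it is probably the intent. It does not remove the problem, because 9.3.2.1 derives its own unqualified value and does not defer to 9.6, and 9.3.1 cannot arbitrate while it gives both values.

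It is also fair to say that the affected group is narrow. Broad disagreement under on-time refills needs a patient who adds a separate ICS, fills one more 28-puff pack and then stops. Triple fixed-dose events and episodes without this pack are untouched.

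A reader might infer that any two 28-puff fills 14 days apart, the index pair included, yield an extra event on every possible add-on day. Sections 9.2.1 and 9.2.2 do not support that. If the two fills are the index fills, triple therapy recognised from days 0 to 13 starts before follow-up, and the patient is excluded instead of counted as an event.

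**Conclusion.** The inconsistency is in the current text and reaches the primary outcome. Followed literally, 9.3.2.1 gives a different event status from 9.6 for some episodes of LAMA/LABA combination plus separate ICS that involve the 28-puff pack, mainly in the Tio/Olo arm.

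Under the regular-refill assumptions, the disagreement is complete (14 of 14 add-on days) with one further pack, slight (1 of 14) with none or two, and absent with three. It applies to packs filled from the start of follow-up onward.

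A reader might go on to infer a material bias in the hazard ratio. The documents do not support this: they do not say how many patients used the pack, in what quantity or with what refill pattern. The effect is unknown and may be small. The study size in 9.5 (1856 patients, 141 events) does not use a days' supply and does not change.

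Confidence is high in the textual conflict and the day counts. No claim is made about the size of any effect on the result. The point should be corrected before the outcome is programmed.

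**What to change.** Reconcile Sections 9.3.1, 9.3.2.1 and 9.6:

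1. In 9.3.1, remove the repeated 28-puff entry from the 30-day list and align the product list with 9.6.
2. In 9.3.2.1, replace the free-standing 30-day statement with a reference to the single pack-specific days-supply rule in 9.6.
3. State that this rule serves the overlap test, the exclusion in 9.2.2 for triple therapy before follow-up, and as-treated discontinuation.

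A count of 28-puff users by arm would show how much the point matters, but is optional. Whether the 14-day allowable gap counts towards overlap concerns every product and is a separate clarification.

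The cost is protocol wording only: one deleted list entry, one aligned list, and one cross-reference with its scope stated. It needs no new data and no change in sample size.
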